5.5 Study Evaluations

5.5a. Study flowsheet

	Procedure	Screen	Baseline M 0	M 3	M 6 M 12 M 18	M 24
Consent		x				
Medical hist	ory	x				
General me	dical exam	x				
Inclusion/Ex	clusion review	x	x			
Safety labs ^a	Safety labs ^{ab}		Xc	Х	X ^h	х
Randomizat	ion		Xa			
Vital signs		x	x	Х	x	Х
Concomitant Medications		x	x	Х	x	Х
T25FW		x	x		x	х
9 HPT		x	x		x	Х
2MTW		x	x		x	Х
EDSS		x	x		x	х
	SDMT		x		M12 only	Х
Cognitive tests	CVLT-2ed		x		M12 only	Х
10313	BVMT-R		x		M12 only	Х
Patient reported outcome measures	PROMIS – pain intensity		x		x	х
	PROMIS – pain interference		x		x	Х
	PROMIS- participation in social roles		X		X	Х
	PHQ-9		X		x	Х

SS-MOS		Х		Х	Х
MFIS		x		x	х
FESI		Х		M12 only	х
GLTEQ		Х		x	Х
Fall count			x		Х
MRI		Xe			Xe
SBQ-R	Х	x	х	х	х
Adverse event monitoring & compliance review ^d		Х	х	x	х
Investigational drug dispensing		Х	x	x	
Subject/provider blinding questionnaire					х
Subject compensation	Х	X	x	x	х
Subject disposition ^f					х
Length of visit (hours)	3	4	1	3	4

BVMT-R, Brief Visuospatial Memory Test- Revised; CVLT-2ed, California Verbal Learning Test- Second Edition; EDSS, Expanded Disability Status Scale; FESI, Fall Efficacy Scale-International; GLTEQ, Godin Leisure-Time Exercise Questionnaire, modified; MRI, magnetic resonance imaging; MFIS, Modified Fatigue impact Scale; 9 HPT, 9 Hole Peg Test; PHQ-9, Patient Health Questionnaire-9; PROMIS, Patient Reported Outcome Measures Information Systems; SBQ-R, Suicide Behaviors Questionnaire-Revised; SDMT, Symbol Digit Modalities Test; SS-MOS, Sleep Scale from the Medical Outcomes Study; T25FW, Timed 25 Foot Walk; 2MTW, 2 Minute Timed Walk

^aIncludes pregnancy test for female subjects of childbearing potential only ^b Optional Biorepository #2916 participation

^cOnly pregnancy test for female subjects of childbearing potential.

^dOccurs at study visits and approximately halfway between each visit after baseline by telephone calls

^eMRIs scheduled up to 14 days prior to M0 and up to 14 days prior to M24 visits. MRIs can be same day as M0 and M24 visits.

^fOccurs at visit M24, at final visit for early termination, and when a subject is determined lost to follow-up.

^gMay occur prior to M0 visit day, when appropriate for logistical purposes, to avoid excessive M0 study visit times.

^hUrine protein additionally tested M9, M15, M21.

5.5b. Consent, medical history, general medical exam: The ICF will be presented by the PI, LSI, or designated study staff. After consent has been obtained, the rest of the study procedures can occur. The medical history and general medical exam is conducted by the treating neurologist for the purpose of eligibility.

5.5c. Vital signs: Resting blood pressure, pulse, and weight are collected by trained study staff at every study visit for the purpose of initial eligibility and ongoing health monitoring. Consistent methods of obtaining data (e.g. same resting period prior to blood pressure and pulse assessments, etc.) is encouraged across study visits. Height is assessed at the screening visit only.

5.5d. Concomitant medication review: Current use of prescribed scheduled and as needed medications as well as over the counter medications and supplements is recorded by the study staff and reviewed at the screen visit by the treating neurologist for study eligibility. Concomitant medications are reviewed at each subsequent visit by study staff and changes reviewed by the treating neurologist. Any start, stop, or change to MS disease-modifying therapies will be noted and dated for data analysis purposes. Supplements will be reviewed by research staff in case they contain lipoic acid or other potential confounders to the study results.

5.5e. Safety laboratory analyses: Laboratory studies will be collected from all subjects at the screening visit if not available within the prior 3 months for establishing eligibility. Additional laboratory analyses occur at visits M3, M6, M12, M18 and M24 to monitor blood cell count, renal function, liver function, urine protein, non-fasting blood glucose levels, HbA1c, and (for women of child-bearing potential) pregnancy testing. Subjects must have urine protein monitored every 3 months for the duration of the study. Pregnancy testing is additionally conducted at the baseline visit for women of child-bearing potential. This involves taking approximately 15-25 mL (3 to 5 teaspoons) of blood at each draw for a total of 90-150mL (2/3 cup) over the course of the study. Laboratory draws will be performed by trained phlebotomists using universal precautions.

5.5f. Inclusion/Exclusion review: Eligibility criteria are reviewed by the treating neurologist during the screening visit. Once all criteria are met and confirmed at the baseline visit, the study staff will use REDCap to assign a randomization code and then

request study drug using the blinded randomization code. For logistical purposes, this may occur prior to M0 visit day to avoid excessive M0 study visit times. Each site pharmacy will then dispense the drug according to the assigned treatment on the randomization schedule, which will be located at each site pharmacy. Subject screens who do not meet inclusion/exclusion requirements will be accounted for in the recruitment monitoring process (See 5.2 Recruitment Methods).

5.5g. Walking tests. The T25FW and 2MTW will be collected at the screening and baseline visits, and every 6 months during the study (21, 22). For the T25FW, subjects are instructed to walk 25 feet marked on the ground "quickly but safely" (Appendix F). The measure is immediately repeated and the two results averaged. Assistive walking devices including canes and walkers are permitted. The 2MTW determines the distance a participant walks in 2 minutes. Dalfampridine is an FDA-approved symptomatic treatment for improving walking speed in MS. Subjects will be asked to maintain their usual dose of dalfampridine at all study visits. Subjects will be strongly encouraged to use the same assistive devices (insoles, orthotics, canes, walkers, etc.) if used at the study start throughout the remainder of the study as safely possible. Subjects who become unable to complete the mobility testing during the course of the study due to worsening MS will continue the study and be analyzed as having worsening mobility according to the data analysis plan. Subjects who are unable to complete mobility testing for non-MS related reasons will not have data recorded for that study visit. Because gait testing is the primary outcome measure, subjects should be tested as early as possible during each study visit. Testing conditions should be as uniform as possible from visit to visit (see 5.1 Study Design, Study timeline and visit scheduling).

5.5h. EDSS: The EDSS is an eight functional system scale to assess overall MS disability including motor, sensory, cerebellar, brain stem, visual, mental, sphincteric, and other systems (24). Each functional system is graded from 0 (no disability) to 5 or 6 (maximal disability). An integrated score between 0 (normal examination) and 10 (death from MS) is formed based on the score in each functional system. The EDSS exam will be performed by a blinded and trained EDSS examiner who is not the subject's usual treating neurologist (Appendix G).

5.5i. 9HPT: The 9 Hole Peg Test (9HPT) is a timed test of upper extremity arm and hand function. Subjects place pegs into a platform with hole and then take them out again (Appendix F). The 9HPT and T25FW will be administered in accordance with the instructions for the Multiple Sclerosis Functional Composite (21).

5.5j. Cognitive tests: Cognitive testing will utilize the Brief International Cognitive Assessment for MS (BICAMS (25) which includes the Symbol Digit Modalities Test (26) (Appendix H), the California Verbal Learning Test- Second Edition (27) (Appendix I),

and the Brief Visuospatial Memory Test- Revised (28) (Appendix J). These measures will be assessed at baseline, M12 and M24.

5.5k. Patient-reported outcome measures: The Patient Reported Outcome Measures Information Systems (PROMIS) will pain intensity (Appendix K), pain interference (Appendix L), and ability to participate in social roles (Appendix M) (29). Additional measures of depression (Patient Health Questionnaire-9, Appendix N), sleep the previous 4 weeks (Sleep Scale from the Medical Outcomes Study, Appendix O), exercise (Godin Leisure-Time Exercise Questionnaire, modified, Appendix V), and the Modified Fatigue impact Scale (Appendix P) will be administered at baseline and every 6 months thereafter (30, 31). The Fall Efficacy Scale-International (FESI) (Appendix T) is administered annually.

5.51. Fall count: Fall count will be kept by a daily Fall Count Diary (Appendix Q). Each calendar page will cover 1 month and will include space to count falls and fall-related injuries each day. Each page will include the definition of a fall as "any unexpected event that results in you ending up on the ground, floor, or any lower surface" (23). At the baseline visit, subjects will be given calendars to cover the first 3 months. Subjects will be called once at the between visit telephone call to encourage falls calendar reporting and have the opportunity to answer any fall counting related questions. A final 3 month supply of falls calendars will be mailed before the end of the study with a target start date on the calendar corresponding to 3 months prior to the final study visit. Subjects will again be called once to encourage compliance and answer any related questions.

5.5m. MRI procedures.

- a. MRI acquisition protocol: A 3T MRI will be utilized to acquire the following series of the brain. 1. A high resolution Magnetization Prepared Rapid Acquisition Gradient Echo (MPRAGE) for high resolution structural (T1-weighted) information, as the basis for brain atrophy measures. Partitions will be 1.0 mm; voxels 1 mm³. 2. Conventional brain imaging with T2-weighted, and FLAIR series; 2mm (non-gapped) slice acquisition, with in plane resolution 1mm². Intravascular MR contrast will not be administered. 3. The American College of Radiology phantom scan will be utilized as necessary for quality control. The imaging procedure will require 60 minutes with approximately 30 minutes participant scan acquisition time, 10 minute phantom scan acquisition time (when needed), and the remaining 20 minutes for positioning and questions. Careful screening of subjects prior to MRI will be done to reduce the chance of injury due to MRI-contraindicated conditions.
- b. MRI clinical readings. MRIs will receive a clinical read from site clinical radiology staff and results reviewed by site treating neurologists for concerning findings

(tumor, stroke, etc.) which, if found, will be communicated to the appropriate clinical service for optimal management including treatment of MS exacerbations.

- c. MRI volumetric analyses: MRI analyses used for study outcomes will be analyzed by the Central MRI Reading Site at OHSU. MRI images are sent to the Reading Site via secure methods. Prior to analyses, AIRC staff will ensure that only the study ID and PHI element of date of study visit are visible to the analysts to reduce any bias. Brain volume measures will be based on SIENAX software and brain atrophy measures on SIENNA tools in the FSL software library produced by the Oxford Centre for Functional MRI of the Brain (32). Total brain T2-hyperintense lesions will be determined using in-house software. In-house and FSL software will be used to explore differential gray versus white matter atrophy as an exploratory MRI outcome measure. Study MRIs will be reviewed for quality within 2 weeks of receipt in order to rescan a subject (1 rescan per subject per MRI visit permitted) if needed within an acceptable time-frame.
- d. MRI quality control (QC): In order to ensure high quality and comparable images across study sites, the Central MRI Reading Site will coordinate QC by having each site perform test scans prior to study start and after every scanner upgrade during the study to review for image quality. In addition, each site will conduct standard phantom scan according to protocols set by the American College of Radiology. Feedback from the Central MRI Reading Site staff to the study sites regarding test, phantom QC, and study MRIs will occur in a timely manner so that errors can be fixed promptly.

5.5n. Suicidality monitoring: Monitoring suicidality is a requirement by the Food and Drug Administration for all neurology studies involving an IND. Monitoring using the with the Suicide Behaviors Questionnaire-Revised (SBQ-R) occurs at the screen to establish a baseline and every subsequent study visit to evaluate for the development of new suicidality (Appendix R).

5.50. Adverse event (AE) monitoring: This occurs at baseline, every subsequent visit, at between visit telephone calls, and *ad hoc*. Unscheduled visits will occur to evaluate AE per the protocol guidelines (sec. 5.1d). AE are coded by the DCC according to MedDRA and reported per the reporting guidelines (sec. 6.0).

Subjects will be encouraged to remain in the study through study completion if they start, stop, or switch a DMT, if their disability progresses due to MS to an EDSS of more than 6.5, or if they have an MS relapse. Subjects who develop MRI contraindications may continue through the study end without further MRIs. Study staff will review eligibility at study visits and during regularly scheduled meetings.

5.5p. Investigational drug dispensing: Drug dispensing occurs at baseline and every study visit according to dispensing schedules by the site research pharmacies.

5.5q. Subject/provider blinding questionnaire: All blinded study staff and subjects take a blinding questionnaire at M24 to evaluate the blind (Appendix S).

5.5r. Subject disposition form: Final disposition of each subject is recorded on this form at the M24, early termination visit, or when determined that the subject is unable to attend an early termination visit.

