Study Design: Participants with primary progressive and secondary progressive multiple sclerosis (MS) will be randomized on a 1:1 basis to LA or placebo. Subjects will complete 7 study visits over 2 years. Walking tests and secondary outcome measures will be performed at every visit. MRIs will be completed at baseline and study end. Safety laboratory measures will be collected at every study visit. The sample size of 59 per arm will allow for a 25% drop-out rate.

List of Abbreviations

ACR, albumin to creatinine ratio

AE, Adverse Event

AIRC, Advanced Imaging Research Center

ALP, alkaline phosphatase

ALT, alanine aminotransferase

AST, aspartate aminotransferase

BBB, blood brain barrier

BDP, Biostatistics & Design Program

BND, Biorepository for Neurological Diseases

CCC, Clinical Coordinating Center

CDA, Career Development Award

CFR, Code of Federal Regulations

CNS, central nervous system

DCC, Data Coordinating Center

DMT, disease-modifying therapies

DSMB, Data Safety and Monitoring Board

EAE, experimental autoimmune encephalomyelitis

EDSS, Expanded Disability Status Scale

eGFR, estimated glomerular filtration rate using MDRD calculation

FESI, Falls Efficacy Scale-International

FDA, Food & Drug Administration

GGT, gamma-glutamyl transferase

GI, gastrointestinal

GLTEQ, Godin Leisure-Time Exercise Questionnaire, modified

ICF, informed consent form

IND, Investigational New Drug

IRB, Institutional Review Board

LA, lipoic acid

LSI, local site investigator

M, month

MDRD, Modification of Diet in Renal Disease

MedDRA, Medical Dictionary for Regulatory Activities

MPRAGE, Magnetization Prepared Rapid Acquisition Gradient Echo

MS, multiple sclerosis

NMSS, National Multiple Sclerosis Society

OCTRI, Oregon Clinical & Translational Research Institute

OHSU, Oregon Health & Science University

PCBV, percent change brain volume

PCP, Primary Care Provider

PD, Protocol Deviation

PHI, protected health information

PMS, progressive multiple sclerosis

QC, quality control

RCT, randomized controlled trial

RIC, Recruitment Innovation Center

RRMS, relapsing-remitting multiple sclerosis

SAE, serious adverse events

SBQ-R, Suicide Behaviors Questionnaire-Revised

SC, Subcutaneous

SCC, Statistical Coordinating Center

SDMT, Symbol Digit Modalities Test

SIENA, Structural Image Evaluation using Normalization of Atrophy

SPMS, secondary progressive multiple sclerosis

T, Tesla

T25FW, Timed 25 Foot Walk

UP, Unanticipated Problem

Synopsis	3

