5.0 Study Procedures

5.1 Study Design

5.1a. Design and specific aims: This is a phase 2, double-blind, multi-center RCT to compare the daily administration of 1200 mg oral LA to a placebo, as a disease-modifying treatment in PMS. A total of 118 subjects with PMS will be randomized 1:1 to LA or placebo. None of the study procedures involve usual care. All study procedures will be covered by study funding.

5.1b. Study population: A convenience sample of adults with PMS will be recruited from the study sites. The multi-site design of the trial is intended to promote generalizability of the study results.

5.1c. Study timeline and visit scheduling. The anticipated study recruitment period is for the first 18 months once the study is approved at the first study site or until enrolment is completed, whichever occurs first. The study will end when the last participant exits the study. There should be no more than 60 days inclusive between the screen and baseline visits. Subsequent study visits will occur at 3 months, 6 months, and every 6 months thereafter, each visit within +/- 2 weeks from the ideal visit based on the baseline/month zero (M0) visit. The MRI can take place up to 2 weeks prior to the baseline and final visits. Should the final MRI be postponed for any reason until after the

final visit, the subjects should continue taking study drug until the MRI has been done. Reasons for conducting visits outside the scheduling window are recorded.

Performance on clinical measures may be subject to variation due to the day-to-day fluctuations characteristic of PMS. Effects of fluctuations on study outcomes will be minimized by encouraging subjects to maintain their usual sleep, eating, and medication intake patterns on study days. Study visits will be scheduled at the same time-period each visit (morning versus afternoon). Study visits may be postponed for concurrent non-MS related illness affecting neurological performance on the discretion of the treating neurologist.

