Risks of study procedures and loss of confidentiality: There is a risk of falls and injury during gait testing. The MRI magnet can cause metal in the body to move, heat, and cause injury. The MRI space is small, so those with claustrophobia are at risk of discomfort during the study. There is a risk of psychological harm from incidental findings unrelated to the study found on MRI such as brain tumors, stroke, other. The risks of blood draws include discomfort, vasovagal syncope, bleeding, bruising, and infection. The risks of clinical testing and patient-reported outcome measures include psychological discomfort from discovering or reporting deficits due to MS. There is a risk of loss of confidentiality of the study data.

5.1m. Protection from risks: The informed consent process will inform potential subjects of the risks of participation. The study will be conducted with IRB oversight. Procedures in this study were specifically designed to minimize risks to the subjects. The investigators will adhere to the Data and Safety Monitoring Plan (sec. 6.2). Trained study personnel will perform all data collection, and information will be coded with a subject identifier to protect subject confidentiality. Findings that could affect the subjects' health or welfare will be reported to the appropriate authorities (e.g. IRB) and communicated to the subjects and appropriate medical service(s) which could include the primary care physician.

Risks to subjects from LA will be minimized by excluding unsuitable patients from enrollment, reviewing medical histories and medications at each study visit for potential interactions with the investigational drug, reviewing AEs for relation to investigational drug, and requiring unscheduled visits for AE evaluation and management.

To minimize the possible GI side effects of oral LA, we recommend subjects take the investigational drug with food, or if necessary, to divide the daily dose, or the dose

reduced by 50% at the discretion of the treating neurologist. Serum renal panels and urinalyses will monitor for kidney damage at every visit.

Trained phlebotomists will perform blood draws to minimize the associated risks of blood draws. Safety monitoring laboratory panels will monitor for liver, kidney, and hematological problems, pregnancy for women of childbearing potential and changes in HbA1c.

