a. Proteinuria monitoring: Subjects must have urine protein *monitored every 3 months* for the duration of the study. Subjects must pause study drug if they skip or miss a visit until draw can occur.

Subjects with baseline (screening) negative or trace proteinuria may participate in the study. Subjects with baseline 1+ or higher proteinuria are further tested for albumin to creatinine ratio (ACR): 1) ACR \leq 300mg/g may participate, 2) ACR >300mg/g are excluded and receive referral to PCP. No repeat screening for proteinuria in subjects who have ACR >300mg/g will be done.

Subjects who experience 1+ or higher proteinuria during the study are further tested for ACR: 1) ACR \leq 300mg/g may continue participation, 2) ACR >300mg/g permanently stop study drug and receive referral to PCP or nephrologist along with notification of the Medical Monitor. A referral to Nephrology is recommended if ACR>1000mg/g. A kidney biopsy is recommended if proteinuria >300 does not resolve within 6 weeks of drug cessation.

b. Renal function monitoring: Subjects with baseline eGFR ≥ 60 may participate in the study. Subjects with baseline eGFR<50 are excluded. Subjects with baseline eGFR 50-59.9 are retested: 1) eGFR ≥ 60 may participate in the study, 2) eGFR<60 are excluded.

Subjects who experience eGFR 50-59.9 during the study are retested within 1 month: 1) eGFR \geq 60 may continue participation in the study, 2) eGFR<60 permanently stop study drug and are referred to PCP. Subjects who experience eGFR<50 during the study permanently stop study drug and referred to PCP. Regardless of the eGFR, if the eGFR decreases by 25% or more compared to the baseline eGFR, the Medical Monitor should be notified and should review the information to determine the next course of action.

c. Liver function monitoring: Abnormal liver laboratory results are graded according to the Common Terminology Criteria for Adverse Events v5.0 (https://ctep.cancer.gov/protocoldevelopment/electronic_applications/ctc.htm).

Subjects who have stable and asymptomatic baseline Grade 1 abnormal laboratory liver values may, at the discretion of the site treating neurologists, participate in the study. Subjects who experience laboratory abnormalities of Grade 1 during the study will be permitted to continue at the full dose of study drug unless advised otherwise by the DSMB or other monitoring entities.

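### Baseline urine protein, eGFR and liver values may be about 5 months old at M0, where no safety panel is drawn although the plan promises one at every visit

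*Combined protocol and SAP*

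**What the plan says.** Four places set the timing of laboratory samples at entry.

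- Section 5.5e makes the screening sample conditional: "Laboratory studies will be collected from all subjects at the screening visit if not available within the prior 3 months for establishing eligibility".
- Section 5.1c sets the interval that follows: "There should be no more than 60 days inclusive between the screen and baseline visits".
- For M0, footnote c of the flowsheet (5.5a) lists a pregnancy test and nothing else under safety labs. Section 5.5e agrees: "Pregnancy testing is additionally conducted at the baseline visit for women of child-bearing potential".
- The later panels are given in 5.5e: "Additional laboratory analyses occur at visits M3, M6, M12, M18 and M24 to monitor blood cell count, renal function, liver function, urine protein". M0 is not among them. Footnote h adds urine protein at M9, M15 and M21.

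Other places describe the schedule more broadly. The synopsis states: "Safety laboratory measures will be collected at every study visit". Section 5.1m states: "Serum renal panels and urinalyses will monitor for kidney damage at every visit", and says the same of glucose and HbA1c. Section 5.5e adds: "Subjects must have urine protein monitored every 3 months for the duration of the study".

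The entry value is used again later. Section 5.1m treats baseline proteinuria as the screening result, and calls for Medical Monitor review "if the eGFR decreases by 25% or more compared to the baseline eGFR". The footnote to 6.3a requires reporting of any new ACR above 300 mg/g, any new eGFR below 60, and ALT or AST grade increases after Screen. Section 5.6b compares laboratory changes from baseline between arms.

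**The concern.** Kidney injury is the drug risk that the protocol itself identifies. Section 2.0 attributes a biopsy-proven glomerulonephritis and a case of proteinuria in the pilot trial to lipoic acid, and 5.1l lists both kinds of event as risks. The reference value for renal safety should therefore describe the participant close to the start of treatment.

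As written, a participant can qualify on an existing result, wait for M0 and begin treatment with no renal or urine test in between. If proteinuria or a fall in eGFR arose in that time, it first shows at M3. It can then be reported as new under 6.3a, trigger the 25% review and enter the change-from-baseline comparison as an on-treatment change, in either arm.

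The definition also has a gap. Sections 5.1m and 6.3a presuppose a screening value, while 5.5e allows the screening sample to be skipped. No section says which result then serves as baseline, or that its date is to be recorded.

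**Working it through.** **Inputs.** Maximum age of an accepted result at screening: 3 months (5.5e), taken as 91 days. Maximum interval from screen to baseline: 60 days (5.1c). M0 labs: pregnancy test only (5.5a footnote c; 5.5e). Next full panel: M3, taken as 91 days after M0, with a window of plus or minus 14 days (5.1c). Number of visits: 7 (synopsis). Blood volume: 15-25 mL per draw, 90-150 mL in total (5.5e).

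**1. The plan's own blood total.** Draws = total / volume per draw. 90 / 15 = 6 and 150 / 25 = 6. Six draws match Screen, M3, M6, M12, M18 and M24. The total therefore includes a screening draw and no full draw at M0, which confirms that footnote c is intended and is not a fault in the table.

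**2. Age of the baseline value at M0, worst case.** 91 + 60 = 151 days, about 5 months. With 3 months counted as 89 to 92 days, the range is 149 to 152 days.

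**3. Age at M0 if the sample is drawn at screening.** At most 60 days, about 2 months.

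**4. Interval from a screening draw to the M3 sample.** 60 + 91 = 151 days, or 60 + 91 + 14 = 165 days (about 5.4 months) at the late edge of the window. Removing the exception in 5.5e shortens the entry interval but does not close it.

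**5. The every-visit statements against the schedule.** Of 7 visits, full safety labs fall at 6. When an existing result replaces the screening draw, they fall at 5.

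**6. Where the age of the value matters.** The 25% eGFR rule, the two new-event renal reports and the 5.6b change scores all need a starting value. The rules in 5.1m on ACR above 300 mg/g, eGFR below 50 and confirmed eGFR below 60 use absolute limits, so they do not depend on how old the baseline is.

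**The case against.** The strongest reply is that this is a stacked worst case in a plan that already has safeguards. Anyone sampled at screening has a value at most 60 days old at M0. A baseline eGFR of 50 to 59.9 is retested. A nephrologist monitors abnormal kidney function at entry (4.0), eligibility is reviewed again at baseline, and 6.1 has attribution graded, with the Medical Monitor deciding if it is uncertain. The on-study stopping limits are absolute. All of this stands, and it keeps the point modest. None of it supplies a fresh urine or renal value for a participant whose existing result was normal, or says which sample is baseline.

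A reader might go further in three ways that the documents do not support.

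- **A breach of the 3-monthly urine protein rule.** Adding the pre-dose time gives 151 + 91 + 14 = 256 days between tests. But 5.1m sets that rule beside the instruction to pause study drug after a missed visit, so it can be read as covering time on drug only. Tests at M3, M6, M9 and so on to M24 meet it on that reading, and the 14 days are the ordinary visit window. The conflict with this rule is weak.
- **Extra noise from a different laboratory.** Section 5.5e does not say where existing results come from, and no section says that on-study tests use one central laboratory.
- **Bias between arms.** Baseline age is settled before treatment and allocation is randomised, so it is non-differential.

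**Conclusion.** The point holds in a limited form. The permitted worst case is a baseline urine protein, eGFR and liver panel about 5 months (151 days) old at M0, with no further value until M3. The conflict between the every-visit statements (synopsis; 5.1m) and the M0 schedule (footnote c; 5.5e) is direct and needs no assumption.

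The consequence is a less certain reference for one Medical Monitor review rule, two mandatory renal reports and the laboratory change analysis. Individual renal findings may be counted as on-study when they began before dosing. How often is unknown, because the documents do not say how many participants qualify on existing results.

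The size rests on three assumptions: 3 months is counted back from the screening visit, first dose is close to M0 (the documents fix dispensing at baseline but not the first-dose date), and a month is about 30.4 days. The point does not undermine the efficacy analysis. It is worth acting on because the remedy is cheap and renal harm is the identified risk.

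**What to change.** 1. In 5.5e, make the sample drawn at the screening visit the baseline sample for urine protein, creatinine/eGFR and liver tests. Existing results may be used for pre-screening only.
2. In 5.6b and 6.3a, state that a change from baseline and a new finding are both judged against that dated sample.
3. Section 2.0 shows that the trial was already producing safety data. For participants already enrolled on existing results, record the sample date, so that the age of the reference value is known at analysis.
4. Reconcile the every-visit statements in the synopsis and 5.1m with footnote c and 5.5e for M0. Item 1 alone still leaves up to 60 days to M0 and about 165 days to the M3 sample. How to resolve this is for the sponsor to decide.

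**Cost.** Items 1 to 3 need a short amendment. The screening draw is already in the schedule and in the 90-150 mL total, so they add no visit and no budgeted draw. The downsides are a few more screen failures and the loss of the convenience of existing results. If item 4 were resolved by a full draw at M0, the stated volume would become 7 x 15 = 105 mL to 7 x 25 = 175 mL. If it were resolved by narrowing the wording, there would be no added volume.
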